3.1.10 Days with respiratory failure over the course of 28 days

This is defined as the number of days with respiratory failure from randomization to Day 28.

The number of days with respiratory failure over the course of 28 days includes all respiratory failures within this 28-day period. All days from the start date to the stop date inclusive of each respiratory failure will count as respiratory failure days.

The following rules will be applied for missing data and deaths:

- Unless stated otherwise, if a subject dies (due to any cause) on or prior to Day 28, the number of days from death to Day 28 will be counted as days with respiratory failure.
- If a subject has been discharged from hospital and is known to be alive at Day 28, and there is no evidence that respiratory failure has occurred during this period, the number of days from being discharged to Day 28 will be assumed free of respiratory failure.
- If a subject has been discharged from hospital but dies on or prior to Day 28 and there is no evidence that respiratory failure has occurred during this period, the number of days from being discharged to the last date known to be alive will be assumed free of respiratory failure. The number of days from death to Day 28 will be counted as days with respiratory failure.
- If a subject has been discharged from hospital but dies on or prior to Day 28 and there is evidence of respiratory failure during this period, the number of days from being discharged to the last date known to be free of respiratory failure will be assumed free of respiratory failure. The number of days from the start of respiratory failure to Day 28 will be counted as days with respiratory failure.
- If a subject withdraws from the study or is lost to follow up on or prior to Day 28, the days with unknown respiratory failure status will be considered as follow:
 - If the subject is discharged from hospital at the time they withdraw from the study or are lost to follow up, days from last known status to Day 28 (or date

last known to be alive if death is known, whichever occurs first) will be assumed free of respiratory failure.

- If a subject is in hospital and is not experiencing respiratory failure at the time they withdraw from the study, days from last known status to Day 28 (or date last known to be alive if death is known, whichever occurs first) will be assumed free of respiratory failure.
- If the subject is in hospital and is experiencing respiratory failure at the time they withdraw from the study, days from last known status to Day 28 will be counted as days with respiratory failure.

3.1.11 Days hospitalized over the course of 28 days

This is defined as the number of days hospitalized from randomization to Day 28 .

For a day to be counted as a hospitalized day in this endpoint, the investigator must confirm that hospitalization is clinically indicated. This information is recorded in the CHCSS eCRF each day the subject is hospitalized.

The number of days hospitalized over the course of 28 days includes any readmissions to hospital within this 28-day period. All days from the start date to the stop date inclusive of each hospital admission will count as hospitalized days.

The following rules will be applied for missing data and deaths:

- Unless stated otherwise, if a subject dies (due to any cause) on or prior to Day 28, the number of days from death to Day 28 will be counted as days hospitalized.
- If a subject withdraws from the study or is lost to follow up on or prior to Day 28, the days with hospitalization status will be considered as follow:
 - If the subject is discharged from hospital at the time they withdraw from the study or are lost to follow up, days from last known status to Day 28 (or date last known to be alive if death is known, whichever occurs first) will be assumed free of hospitalization.
 - If the subject is in hospital at the time they withdraw from the study, days from last known status to Day 28 will be counted as days hospitalized.

3.1.12 Days in ICU over the course of 90 days

This is defined as the number of days in ICU (length of stay) from randomization to Day 90 days.

For a day to be counted as an ICU day in this endpoint, the investigator must confirm that the subject is receiving ICU-standard care (or equivalent) and that ICU is clinically indicated.

This information is recorded in the CHCSS eCRF each day the subject is receiving ICU-standard case.

The number of days in ICU over the course of 90 days includes any readmissions to the ICU within this 90-day period. All days from the start date to the stop date inclusive of each ICU stay will count as ICU days.

The following rules will be applied for missing data and deaths:

- Unless stated otherwise, if a subject dies (due to any cause) on or prior to Day 90, the number of days from death to Day 90 will be counted as ICU days.
- If a subject has been discharged from hospital they will be assumed free of ICU.
- If a subject has been discharged from hospital but dies on or prior to Day 90 and there is no evidence of ICU admission during this period, the number of days from being discharged to the last date known to be alive will be assumed free of ICU. The number of days from death to Day 90 will be counted as ICU days.
- If a subject has been discharged from hospital but dies on or prior to Day 90 and there is evidence of ICU admission during this period, the number of days from being discharged to the last date known to be free of ICU will be assumed free of ICU. The number of days from ICU admission to Day 90 will be counted as ICU days.
- If a subject withdraws from the study or is lost to follow up on or prior to Day 90, the days with unknown ICU status will be considered as follow:
 - If the subject is not in ICU at the time they withdraw from the study or are lost to follow up, days from last known status to Day 90 (or date last known to be alive if death is known, whichever occurs first) will be assumed free of ICU.
 - If a subject is in ICU at the time they withdraw from the study, days from last known status to Day 90 (or date last known to be alive if death is known, whichever occurs first) will be counted as ICU days.

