4.5 End of Study Definition

The end of study is defined as the last expected visit/contact of the last subject undergoing the study.

A subject is considered to have completed the study when he/she has completed his/her last scheduled procedure shown in the Schedule of Activities (SoA; Section 1.1). All randomized subjects will be followed for survival through 90 (\pm 7) days after randomization.

All subjects who discontinue the investigational study treatment for any reason other than withdrawal of consent, loss to follow-up, or death will have a safety follow up assessment 28 (\pm 3) days after the last dose of acalabrutinib (Arm 1), or 38 (\pm 3 days) after randomization for those subjects randomized to the BSC arm (Arm 2), as outlined in Section 1.1.

The study may be stopped if, in the judgment of the Sponsor, study subjects are placed at undue risk because of clinically significant findings.

See Appendix A 6 for guidelines for the dissemination of study results.

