3.1.5 Change from baseline in absolute lymphocyte counts

This is defined as the change from baseline in absolute lymphocyte counts at Days 3, 5, 7, 10, 14 and 28. For this endpoint, baseline is defined as the observation on the date of randomization (Day 1). If no result was obtained on the date of randomization, the last result prior to the date of randomization will be used. Details on visit windows are provided in Section 4.1.

The percent change from baseline at these timepoints will also be derived.

3.1.6 All-cause mortality at Day 90

This is defined as the proportion of subjects who have died due to any cause by Day 90.

If a subject is not known to have already died, they (or a caregiver/relative) will be contacted at Day 90 (± 7 days) to confirm survival status. If a subject is lost to follow-up or has withdrawn consent to be followed-up at this timepoint, the survival status of the subject may be obtained by site personnel by checking publicly available resources (as applicable under local laws).

Subjects alive at Day 90 will be censored at Day 90 and subjects lost to follow-up (i.e. with unknown survival status at Day 90) will be censored at the last time known to be alive.

3.1.7 Alive and discharged from the ICU at Days 14 and 28

This is defined as the proportion of subjects alive and discharged from the ICU at Day 14 and the proportion of subjects alive and discharged from the ICU at Day 28.

For a subject to be considered discharged from the ICU, they must not be in ICU on Day 14 (or Day 28), regardless of whether or not ICU-standard care is reported as not clinically indicated in the CHCSS eCRF.

Only the subject's survival status and ICU status on Day 14 (or Day 28) will be considered for this endpoint. No visit window will be used for this endpoint. If they are admitted to ICU after randomization but are discharged by Day 14 (or Day 28), they will be considered alive and discharged from the ICU at Day 14 (or Day 28).

For the FAS analysis, subjects who withdraw or are lost to follow up on or prior to Day 14 (or Day 28), thus survival status and respiratory status at Day 14 (or Day 28) cannot be assessed, will be included in the denominator of this analysis as though they had died or had a respiratory failure.

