3.1.14 Days alive outside of hospital over the course of 90 days

This is defined as the number of days alive outside of hospital from randomization to Day 90.

For a day to be counted as outside of hospital, the subject must not be in hospital. If the subject is in hospital but hospitalization is recorded as not clinically indicated, this day will still be considered as a day in hospital and therefore will not be counted in this endpoint.

The following rules will be applied for missing data:

- If a subject withdraws from the study or is lost to follow up on or prior to Day 90, the days with unknown survival/hospitalization status will be considered as follow:
 - If the subject is discharged from hospital when they withdraw from the study or are lost to follow up, days from last known status to Day 90 (or date last known to be alive if death is known, whichever occurs first) will be counted as days alive and outside of hospital.
 - If a subject is in hospital at the time they withdraw from the study, days from last known status to Day 90 will be assumed hospitalized days.

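### Two 90-day endpoints depend on hospital and ICU readmissions, but no scheduled contact after the safety follow-up asks discharged subjects about them

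*SAP*

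**What the plan says.** Two secondary endpoints run to Day 90 and depend on where the subject is on each day.

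- **ICU days (SAP 3.1.12).** The count "includes any readmissions to the ICU within this 90-day period". Among the rules for missing data and deaths is this default: "If a subject has been discharged from hospital they will be assumed free of ICU".
- **Days alive out of hospital (SAP 3.1.14).** The endpoint is "the number of days alive outside of hospital from randomization to Day 90". It does not mention readmission, but a day counts only if the subject is not in hospital, so a readmission should subtract days. By contrast, the 28-day hospitalization endpoint (SAP 3.1.11) says outright that it "includes any readmissions to hospital within this 28-day period". For subjects who withdraw or are lost after discharge, the remaining days to Day 90 (or to the date last known alive, if death is known) "will be counted as days alive and outside of hospital".

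The follow-up provisions are narrower. Protocol 4.5 states: "All randomized subjects will be followed for survival through 90" days after randomization. SAP 3.1.6 says that subjects not known to have died, "they (or a caregiver/relative) will be contacted at Day 90", and gives the purpose as confirming survival status. In both Schedule of Activities tables the only row marked in the Day 90 column is survival status.

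**The concern.** An endpoint that counts readmissions over 90 days needs some means of learning about them over 90 days. A subject still in hospital is seen every day. A subject who has gone home is seen only at the scheduled contacts, and the last of these before Day 90 is the safety follow-up. If that subject is later admitted elsewhere and survives, nothing scheduled brings the stay to the site's attention, and the scoring rules turn the silence into a good outcome: no ICU days, and full credit for days out of hospital.

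What is at stake is whether these two endpoints are complete in the second half of their period. Unobserved days would be reported in the same way as observed good days, and the reader of the study report could not tell them apart. Late relapse or complications leading to readmission would be under-counted.

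**Working it through.** **The plan's own figures.** The documents give no readmission rate, length of stay or precision for either 90-day endpoint. The only sample-size figures concern the Day 28 primary endpoint (Protocol 9.2), and they reproduce. SE = √(0.7×0.3/30 + 0.9×0.1/30) = √0.010 = 0.100; half-width = 1.645 × 0.100 = 16.45% (stated 16.4%); power = Φ(0.20/0.100 − 1.645) = 63.9% (stated about 64%). Nothing below changes them.

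**What is collected after discharge.**

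1. Daily assessments in the Schedule of Activities run until hospital discharge. The 9-point scale, which separates hospitalized from ambulatory subjects, is scheduled again on Days 14 and 28 but not later.
2. The safety follow-up is 28 (±3) days after last dose in Arm 1 and 38 (±3) days after randomization in Arm 2.
3. AE and SAE reporting ends there. After it, only SAEs judged related to study treatment or procedures are reportable (Protocol 8.6.2), so an unrelated readmission need not appear.
4. Even before that point, SAE reporting is an uncertain route for COVID-19 relapse. Protocol 8.6.10 keeps events unequivocally due to COVID-19 pneumonia out of AE and SAE reporting, while 8.6.9 makes an exception for those meeting SAE criteria.
5. Protocol 8.3 collects admission and discharge dates for all subjects, but under on-study procedures, in the singular, and without naming a later contact.

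**How an unrecorded stay is scored.** SAP 3.1.12 assumes a discharged subject is out of ICU; its provision for evidence of ICU admission after discharge is written for subjects who die. SAP 3.1.14 has no rule for discharged subjects who remain on study. Their days count as out of hospital because nothing is recorded to the contrary.

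**Length of the window without active questioning (90 minus the day of last contact).**

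| Last contact | Days left | Share of 90 |
|---|---|---|
| Day 35 | 55 | 61% |
| Day 38 | 52 | 58% |
| Day 41 | 49 | 54% |
| Day 29 (Arm 1, dosing stopped on Day 1) | 61 | 68% |

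Day 38 is fixed only for Arm 2. In Arm 1 the contact moves with the last dose: dosing that ends on Day 10 puts it at Day 38, and early discontinuation brings it forward (1 + 28 = Day 29 at the extreme, before the ±3 days).

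**Effect on an arm mean.** Error in the mean = proportion with an unrecorded stay × length of stay. The inputs are assumptions:

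- 5% × 7 days = 0.35 days; 15% × 7 days = 1.05 days. Against 90 days these are 0.4% and 1.2%.
- Wider range: 5% × 5 days = 0.25 days; 20% × 14 days = 2.8 days.
- One missed 7-day stay in an arm of 30: 7/30 = 0.23 days. One missed 14-day stay: 14/30 = 0.47 days.

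For ICU days these are ceilings, since only the part of a readmission spent in clinically indicated ICU care counts.

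**The case against.** The strongest reply is Protocol 8.4.3. It has the investigator determine, for each day in hospital up to Day 90, whether the subject is receiving ICU-level care and whether that care is necessary. SAP 3.1.12 says each such day is entered in the eCRF. That is a purpose-built collection procedure with the right horizon, and in-hospital assessments have no Day 38 cut-off.

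The scoring rules are also less one-sided than the ICU-free default suggests. Days from death to Day 90 count as ICU days, and a discharged subject who dies with evidence of an ICU admission is counted in ICU from that admission. The telemedicine footnote attached to the Day 90 column, and Protocol 7.1, mention AEs and concomitant medications at the survival contact. Protocol 8.2 documents medications and procedures to the end of participation. The eCRF pages are not among the documents, so a readmission field may exist.

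Most of this stands, and it rules out three stronger readings that a reader might infer:

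- *That only survival is collected after about Day 38.* Protocol 8.4.3 contradicts this for anyone in hospital under the site's observation.
- *That both endpoints are simply the status at the safety follow-up extended to Day 90.* Continuing stays, readmissions known to the site, and deaths all alter the count.
- *That every late readmission is missed, or that the treatment comparison is biased.* The documents support neither; both would need facts that they do not contain.

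What the reply does not supply is a way for the site to learn of a readmission elsewhere. The daily ICU question applies once the site knows the subject is in hospital. The Day 90 column leaves the AE and concomitant-medication rows unmarked, and no provision for that contact names hospital or ICU status.

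**Conclusion.** The point holds as a gap in finding readmissions after discharge. For subjects discharged alive, nothing scheduled asks about hospital or ICU admission after the safety follow-up, and a stay unknown to the site is scored favourably in both 90-day endpoints.

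The window is about 52 of 90 days with a last contact on Day 38 (49 to 55 across the ±3 days), and longer in Arm 1 after early discontinuation. This is calendar time without active questioning, not the amount of missing data. If 5-15% of subjects had an unrecorded 7-day stay, an arm mean would be off by at most about 0.35 to 1.05 days. Both the rate and the length of stay are assumptions. The direction is known: too few ICU days and too many days out of hospital. The between-arm difference is affected only if missed stays differ by arm.

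Both endpoints are secondary and summarized descriptively (SAP 4.3.2.11 and 4.3.2.13). The primary endpoint, sample size and power are untouched. This is a cheap improvement, not a threat to the study's main conclusion.

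**What to change.** At the safety follow-up and Day 90 contacts, ask the subject, caregiver or relative about any hospital or ICU admission since the last contact: dates in and out, and whether the stay was clinically indicated. Record the answers in the eCRF and use them in SAP 3.1.12 and 3.1.14. State in 3.1.12 that the ICU-free default applies only when no admission is reported, and in 3.1.14 that readmission days are subtracted. Because the Day 90 contact may fall up to 7 days early, say how the days between the contact and Day 90 are scored.

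SAP 1.3 notes that recruitment was already complete, with 62 subjects randomized. For any Day 90 contacts already past, check hospital records retrospectively, or state in the SAP and study report that the two endpoints cover only stays known to the site.

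The cost is one added question and eCRF field at contacts that already take place, plus a protocol amendment, which needs IRB/IEC approval under Protocol Appendix A 1.

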8.4.3 Assessment of Number of Days in ICU

Assessment of ICU length of stay will be obtained by asking the Investigator to determine if the subject is receiving ICU standard care (or equivalent) on each day during hospitalization up to Day 90. In the event of an affirmative response, a further question will be asked to determine if this ICU care is considered necessary (rather than being due to logistical reasons).

Only days in the ICU (or equivalent), which the Investigator considers necessary, will be regarded as ICU days.

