3.1.8 Time to first occurrence of respiratory failure or death

This is defined as the time (in days) from randomization to the first occurrence of respiratory failure or death (due to any cause) on study (up to Day 28), whichever occurs first.

If a subject does not have an event (i.e., does not experience respiratory failure or death) on or before Day 28 and does not withdraw or become lost to follow up from the study on or prior to Day 28, the data will be censored at Day 28. If a subject does not have an event but withdraws from the study or is lost to follow up on or prior to Day 28, the data will be censored at the last date known that the subject was alive and free of respiratory failure up to Day 28.

Subjects with respiratory failure at baseline (defined as respiratory failure on the date of randomization (Day 1)) will not be included in any analyses of time to first occurrence of respiratory failure or death.

Subjects with respiratory failure at baseline (described in Section 3.5.1) will not be included in any analyses of time to first occurrence of respiratory failure or death.

3.1.9 Days alive and free of respiratory failure over the course of 28 days

This is defined as the total number of days alive and free of respiratory failure from randomization to Day 28.

For a day to count as ‘alive and free of respiratory failure’, the subject must be free of respiratory failure for the entire day. All days from the start date to the stop date inclusive of each respiratory failure will count as respiratory failure days. If a subject dies on Day 1, the number of days alive and free of respiratory failure is zero. If a subject is alive on Day 28 and has not experienced respiratory failure at any point over the 28 day period, the number of days alive and free of respiratory failure is 28 days.

The following rules will be applied for missing data:

- If a subject has been discharged from hospital and is known to be alive at Day 28, and there is no evidence that respiratory failure has occurred during this period, the number of days from being discharged to Day 28 will be counted as days alive and free of respiratory failure. If a subject has been discharged from hospital but dies on or prior to Day 28 and there is no evidence that respiratory failure has occurred during this period, the number of days from being discharged to the last date known to be alive will be counted as days alive and free of respiratory failure.

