4.3.2.11 Days in ICU over the course of 90 days

Summary statistics (n, mean, SD, median, minimum and maximum) for the length of stay (days) in ICU over 90 days will be presented by treatment group. In addition, the number and

percentage of subjects in the following categories will be presented, 0 days, 1-6 days, 7-14 days, 15-21 days, 22-28 days and >28 days.

A bar chart of the number of days in ICU for each subject within the treatment group will be produced, i.e., showing graphically the distribution of the number of days in ICU for each treatment group.

The method for handling deaths and subjects that withdraw or are lost to follow up on or prior to Day 90 is detailed in Section 3.1.12.

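### Days after death are scored as ICU, hospital and respiratory-failure days, and the ICU score is then reported as length of stay

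*SAP*

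**What the plan says.** Three secondary endpoints count days in a state, and the SAP gives each the same default for death from any cause:

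- SAP 3.1.10, days with respiratory failure: "the number of days from death to Day 28 will be counted as days with respiratory failure".
- SAP 3.1.11, days hospitalized: "the number of days from death to Day 28 will be counted as days hospitalized".
- SAP 3.1.12, days in ICU: "the number of days from death to Day 90 will be counted as ICU days". A separate bullet applies this to a subject who dies after discharge with no sign of an ICU admission.

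The definition of an ICU day is narrower. Protocol 8.4.3 states: "Only days in the ICU (or equivalent), which the Investigator considers necessary, will be regarded as ICU days". SAP 3.1.12 itself opens by requiring that "the investigator must confirm that the subject is receiving ICU-standard care (or equivalent) and that ICU is clinically indicated".

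SAP 4.3.2.11 then says that summary statistics "for the length of stay (days) in ICU over 90 days will be presented by treatment group". It adds a frequency table with classes 0, 1-6, 7-14, 15-21, 22-28 and >28 days, and a bar chart.

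Protocol 9.5 says that the SAP will specify how death is handled for endpoints without a mortality component. SAP section 7 lists no change from the protocol.

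**The concern.** A reader of the ICU table expects ICU use. The number shown is ICU days plus all time from death to Day 90, whether or not the subject was ever in ICU. The >28 days class mixes long ICU stays with deaths. The 0 days class no longer holds everyone who never used ICU.

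Nor does the score rank death as the worst outcome, because the penalty shrinks as death comes later.

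For respiratory failure, the protocol lists two endpoints: days with it, and days alive and free of it. If the first is the complement of the second, the trial reports one quantity twice and has no measure of time actually spent in respiratory failure.

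**Working it through.** **Inputs from the documents.** Windows of 28 and 90 days and the death rules (SAP 3.1.10 to 3.1.12); the ICU summary and its classes (SAP 4.3.2.11); 30 subjects planned per arm (Protocol 9.2). The plan gives no figure for these endpoints, so there is none to reproduce.

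**Inputs not given, so assumed.** Mortality m (3.3% to 20%), day of death d (10, 14, 21 or 28), proportion ever in ICU a (20%, 30% or 40%), mean real ICU stay L (7, 10, 14 or 21 days). The SAP does not say whether the day of death itself is counted, so a post-death count is 90 - d or 90 - d + 1. I use 90 - d unless both are shown.

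**1. Single subjects.**

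| Subject | Real ICU days | Score under 3.1.12 |
|---|---|---|
| Ward death on Day 5, never in ICU | 0 | 85 or 86 |
| ICU on Days 3 to 12, survives | 10 | 10 |
| Ward death on Day 85, never in ICU | 0 | 5 or 6 |

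These are constructed examples. Since 90 - d > 28 when d < 62, any subject covered by the default rule who dies by Day 61 falls in the >28 days class, with or without ICU care.

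**2. Share of a decedent's score that lies after death.** Even for a subject in ICU every day until death, it is (90 - d)/90: Day 14, 76/90 = 84%; Day 28, 62/90 = 69%; Day 45, 45/90 = 50%. Less ICU time before death makes it larger.

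**3. Share of the arm mean.** Share = m(90 - d) / [m(90 - d) + aL]. The assumed values of d, a and L give 4 × 3 × 4 = 48 combinations at each mortality.

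| m | Lowest (d=28, a=40%, L=21) | Middle (d=14, a=30%, L=10) | Highest (d=10, a=20%, L=7) | Combinations above one half |
|---|---|---|---|---|
| 3.3% | 20% | 46% | 66% | 11 of 48 |
| 5% | 27% | 56% | 74% | 24 of 48 |
| 10% | 42% | 72% | 85% | 43 of 48 |
| 15% | 53% | 79% | 90% | 48 of 48 |
| 20% | 60% | 84% | 92% | 48 of 48 |

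Example, middle column at 10%: post-death days 0.10 × 76 = 7.6 and real ICU days 0.30 × 10 = 3.0. The reported mean is 10.6 days, of which 7.6/10.6 = 72% is post-death.

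**4. Weight of one death.** A Day 14 death adds 76/30 = 2.5 days to the mean of a 30-subject arm.

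**5. Respiratory failure.** SAP 3.1.10 says "All days from the start date to the stop date inclusive of each respiratory failure will count as respiratory failure days", and 3.1.9 uses the same count. For a survivor the two endpoints sum to 28; with no failure, 3.1.9 says that "the number of days alive and free of respiratory failure is 28 days". For a death on Day k after f failure-free days, 3.1.9 gives f. Section 3.1.10 gives (k - 1 - f) days before death plus (28 - k + 1) from death, which is 28 - f. The sum is again 28. If the day of death is counted in both endpoints, the sum can be 29. Small gaps between last known status and death or onset of failure can also shift it.

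**6. Hospital days.** The mirror is only approximate. Section 3.1.11 counts days on which hospitalization is clinically indicated, whereas 3.1.13 treats every day in hospital as a hospital day.

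**The case against.** The strongest reply is that Protocol 9.5 delegates the death rule to the SAP, the rule is prespecified, and penalising death is a recognised composite strategy. Without a penalty, an arm with more early deaths shows fewer ICU, hospital and failure days and can look better. All of this stands. It justifies having a death-penalised score, but not calling it length of stay.

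A reader might infer that ICU length of stay in this trial is mostly time after death. The documents do not support that for an arm, because they give no mortality, timing of death or ICU use. At 5% assumed mortality, half of the combinations fall below one half.

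A reader might also infer that an effect on ICU stay could not be seen at all. That goes too far. If deaths are equal in number and timing, the post-death days cancel in the difference of means. Day 90 mortality and the proportion alive and discharged from ICU are reported separately, and the death rule leaves survivors' scores unchanged. What remains is noise from chance differences in deaths. At 10% mortality and Day 14 deaths, post-death days have a standard deviation of 76 × √(0.1 × 0.9) = 22.8 days per subject. With 30 per arm, that alone gives the difference in means a standard error of 22.8 × √(2/30) = 5.9 days.

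For survivors, the two respiratory-failure endpoints mirror each other by the protocol's own definitions. The death rule only extends this to subjects who die. Finally, these are secondary endpoints summarised descriptively, and Protocol 9.1 plans no formal hypothesis testing.

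**Conclusion.** The point holds as a matter of labelling and coherence. The SAP may set a death rule, but a score that includes post-death days is not ICU length of stay as Protocol 8.4.3 and SAP 3.1.12 define an ICU day. It is not a consistent worst-outcome score either, since a late ward death scores below a survivor with a 10-day stay.

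Three results need no assumed rates: anyone covered by the default rule who dies before about Day 45 has mostly post-death ICU days; one Day 14 death moves a 30-subject arm mean by about 2.5 days; and days with respiratory failure is essentially 28 minus days alive and free of it. The post-death share of an arm mean does rest on assumptions. It runs from 27% to over 80% (92% at the extreme) for assumed mortality of 5% to 20%, so the mean may be mostly post-death time, but this cannot be asserted in advance. The primary endpoint is unaffected.

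**What to change.** - In SAP 4.3.2.9 to 4.3.2.11, report observed days while alive, counted to death or the end of the window, next to the number of deaths in each arm.
- Show deaths as a separate category in the frequency tables and bar charts.
- Keep the death-penalised versions, but call them composites and summarise them by the median. The median may be 0 for ICU if fewer than half of an arm used ICU or died, so the frequency table must carry that result.
- If a composite is meant to rank death worst, give every death in the window the same worst value. State whether the day of death is counted.
- Record the death rule in SAP section 7.

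The cost is SAP wording and one extra derived variable per endpoint, with no new data collection. The downside is real: early death shortens observed stays, so those tables must be read with mortality. The existing days-alive endpoints (SAP 3.1.9, 3.1.13 and 3.1.14) help with that for respiratory failure and hospital stay.
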